For patients who lack the capacity to consent, the investigator/designee may explain the study to the legally authorized representative by phone. The discussion will be documented in the subject's medical record or research chart. Two copies of the unsigned consent form will be sent to the subject/legal representative with instructions for completion of the signature page and assent (if applicable). Signatures will be obtained according to standard Baylor IRB regulations. The subject will be told to keep one form and returned the other to the investigator by mail, email, or fax. The Baylor Investigator/designee will sign the consent form when returned from the subject. The signed consent form will be maintained in research records.

E3. Pregnant woman/fetus

Will pregnant women and/or fetuses (as described in 45 CFR 46 Subpart B) be enrolled in the research?

No

E4. Neonates

Will neonates of uncertain viability or nonviable neonates (as described in 45 CFR 46 Subpart B) be enrolled in the research?

No

E5. Children

Will children be enrolled in the research?

No

Section F: Design/Procedure

F1. Design

Select one category that most adequately describes your research:

c) Pilot

Discuss the research design including but not limited to such issues as: probability of group assignment, potential for subject to be randomized to placebo group, use of control subjects, etc.

Phase I: 20 subjects with COVID-19 infection that are being treated in the hospital. This means that this patient population is positive to COVID-19, are hospitalized, or develop severe symptomatology, but they have been admitted with no more than 48 hours to the hospital. Also, in some cases the patients will not be able to consent at the time of enrollment determines a high grade of severity of illness. The entire cohort will receive daily electrical stimulation in lower extremity (e.g. Gastrocnemius, tibial anterior muscle) up to 1 hour to decrease Neuromyopathy complications and prolonged hospital stay. Due to the condition of the patient we are looking to reduce the interaction with staff, the device will be placed with no additional requirements. Physical therapy targets other physical performances, this device is aimed to improve blood flow, tissue perfusion and muscle activation while the patient is non-responsive to physical activities.

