Aim 2 (to examine effectiveness): Examine effectiveness of daily use of EE to treat CINM, and other associated major adverse events (MAE) including deep vein thrombosis (DVT), cardiovascular events, and death. Participants will receive standard of care plus adjunctive daily EE therapy using an FDA approved bio-electric stimulation technology (BEST) platform (Tennant Biomodulator® PRO, AVAZZI A, Inc) during the entire length of stay in hospital. The device will be provided by the research staff.

We will assess incidence of neuropathy and myopathy during hospital discharge or 4 weeks, whichever comes first. Neuropathy severity will be quantified using vibratory perception threshold (VPT) test. Myopathy will be assessed by measuring changes in calf muscle circumference, weight change from pre-hospital admission, and sEMG. In addition, we will determine weakness using foot dynamometer and a validated frailty meter. Length of hospital stay and MAE (documented via electronic health record) will be tracked for planning of future studies. Both extremities will have all measurements and 1 hour electrical stimulation therapy at baseline. Daily treatment will be performed up to 3 times per day, but no more than 1 hour in total.

Daily electrical stimulation will be administered by a nurse/staff involved in the hospital care. A chart will be signed to register each therapy performed and will include a log of day and time of device application.

Both electrical stimulation and EMG devices will have disposable pads, after usage they will be discarded. For the Devices

they will be placed inside a plastic bag that will be disposed inside the room before exiting and sanitized (wipes) based upon hospital protocols.

The researchers will take digital photographs /videos throughout the study. This is done using a special camera for tissue oxygen detection and visual images. This method is non invasive and does not cause any harm to the patient. **We will blur the face out in the photographs/videos. We will only use videos and photos for scientific presentations or scientific publications.

Phase II:

Patients will begin the study after being diagnosed with neuromyopathy due to prolonged hospitalization for COVID-19. This will be performed by a critical care and pulmonary specialist at the BCM COVID-19 Clinic.

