The protocol will consist of 4 weeks of lower-extremity electrical stimulation. Opposite to our initial study, this modality will consist of home-based therapy, meaning that the patient will take the device home and attend the clinic once a week for screening and assessment of therapy.

The protocol will be performed as the following description: This trial will have 20 patients divided in two groups. Group 1 (intervention, n=10): Will receive an active Tennant Biomodulator Group 2 (control, n=10): Will receive an inactive Tennant Biomodulator This study will consist of 5 visits total and one phone interview 12 weeks after baseline for both groups. The patient will be compensated \$50 per visit (total \$250), with free parking. Payment will only be available for subjects who participate in Part II.

During the first and last visit, the research staff will turn the Tennant Biomodulator PRO® on for one hour and measure any changes in muscle strength, endurance, and blood flow after the therapy. Once the first visit is over, the patient will take the Tennat Biomodulator® home and will be instructed to turn it on for one hour every day for four weeks.

The visits in-between will be performed in the following order: 1) Questionnaires (pain, weakness, sleep, quality of life, frailty, depression, life and space, beck anxiety scale, Katz-daily living) 2) Musculoskeletal assessments (non-invasive surface electromyography, vibration perception threshold) 3) Vascular assessments (non-invasive Near infra-red spectroscopy)

After 4 weeks, the patients will turn back the device to the research staff.

The supervision of this study will be by pulmonary care specialists, and the location will be at the recently open COVID-19 clinic at Baylor College of Medicine.

Section G: Sample Size/Data Analysis

G1. Sample Size

How many subjects (or specimens, or charts) will be used in this study?

Local: 40 Worldwide: 40

Please indicate why you chose the sample size proposed:

Sample size is convenient and selected based on available resources to demonstrate feasibility and the proof of concept effectiveness of EE therapy for COVID-19 patients admitted to ICU and post-ICU. We plan to recruit 40 eligible subjects.

G2. Data Analysis

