Describe potential benefit(s) to be gained by the individual subject as a result of participating in the planned work.

There is potential benefit of prevention or improvement of hospital acquired weakness due to prolonged hospital stay for participants, based on previous studies the electrical stimulation will improve blood flow, tissue perfusion and muscle activation. The device is used to reduce pain. However, the proposed treatment may assist in preventing or improving hospital-acquired Weakness because of prolonged hospital stay . In addition, the participation in this study may help the investigators better understand how COVID19 may impact cause myopathy and neuropathy and how to best help these patients to recover from prolonged hospital-stay .

Primary outcomes include neuropathy (assessed using VPT test); muscle function (assessed using sEMG), and tissue oxygenation (assessed using Kent Imaging). Secondary outcomes include weakness (assessed using dynamometer); muscle atrophy (assessed by weight loss as well as measuring ankle, calf, and thigh circumference); venous return flow (Doppler US [optional]); frailty (frailtymeter [optional]); hospital length of stay (patient medical record); and major adverse events (patient health record). The primary and secondary outcomes will be assessed at baseline (if feasible) and on biweekly basis up to 4 weeks or hospital discharge, whichever came first. Appropriate mixed models (linear for continuous or Generalized Estimating Equations (GEEs) for non-continuous or non-parametric variables) will be used to test the intervention effect for each of the primary (e.g., tissue perfusion, tissue oxygen delivery, neuropathy severity, and

myopathy incident) or secondary (e.g., frailty, weight loss, MAE, etc) outcomes.

Also, participation may help the investigators design a practical assessing method to identify the impact of neuromyopathy in the hospital setting. This may allow physicians to provide personalized care by monitoring muscle loss and limb complications caused by prolonged hospital length of stay.

Describe potential benefit(s) to society of the planned work.

As described above, this type of work may allow physicians to provide more personalized care for hospitalized patients in need of physical therapy for continuous and prolonged periods, specially when having a severe illness that includes medical staff risk contact.

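### Major adverse events are routed to a GEE test that, in its usual form, reports a very small p-value whenever exactly one arm has no event

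*Protocol*

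**What the plan says.** Protocol Section I (Potential Benefits) sets the method for outcomes that are not continuous: "Generalized Estimating Equations (GEEs) for non-continuous or non-parametric variables) will be used to test the intervention effect". The outcomes it covers include "or secondary (e.g., frailty, weight loss, MAE, etc) outcomes". A yes/no MAE outcome is therefore assigned to GEE.

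Protocol Section F2, Phase I Aim 2, defines "major adverse events (MAE) including deep vein thrombosis (DVT), cardiovascular events, and death". The same aim then gives MAE a more modest role: "Length of hospital stay and MAE (documented via electronic health record) will be tracked for planning of future studies".

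On the groups, Section F1 describes "Phase I: 20 subjects with COVID-19 infection that are being treated in the hospital", all of whom receive stimulation, with no control group. Section F2, Phase II, says "This trial will have 20 patients divided in two groups" and gives their sizes: "Group 1 (intervention, n=10): Will receive an active Tennant Biomodulator Group 2 (control, n=10): Will receive an inactive Tennant Biomodulator". The SAP uses GEE with two groups (CG and IG), three times and their interaction. It states no number per group and does not name MAE.

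Section G2 sets two-sided significance at p of 0.05 or less. Neither document states the link, the variance estimator, the type of test, or an exact or penalised fallback. The SAP's chi-square test is for baseline comparisons only.

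**The concern.** MAE are likely to be few in groups this small, and death cannot recur. An arm with no event is then a realistic result. In a logistic model, an empty arm makes the log odds ratio infinite, so the software stops at some large finite value. The robust standard error does not grow with it; it settles near 1. The Wald ratio is then very large and the p-value extremely small, even when the data hold one event.

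At stake is a false statement about deaths, DVT or cardiovascular events, in either direction: an apparent harm or an apparent benefit. MAE belong to the effectiveness aim and are meant to inform later studies, so a spurious p-value could carry forward into that planning.

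**Working it through.** **Inputs.** Method and outcome list: Section I. Components of MAE: Section F2, Phase I Aim 2. Arms of 10 and 10: Section F2, Phase II. Significance level: Section G2. Event risk: not given, so a range is assumed. The documents state no p-value, event rate or power for MAE, so there is no figure of theirs to reproduce. The total of 40 (20 + 20) is a convenience size under Section G1.

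**Step 1: standard error when one arm is empty.** In an arm of n patients with no event, the robust variance of the logit tends to 1/n. In the other arm, with event proportion m, it is 1/(n·m·(1 − m)). For 0/10 v 1/10:

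SE = √(1/10 + 1/(10 × 0.1 × 0.9)) = √(0.100 + 1.111) = 1.10.

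The fitted log odds ratio stopped at 21.4 in absolute size, so z = 21.4/1.10 ≈ 19.4.

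**Step 2: same data (0/10 v 1/10, one record per patient), different settings.**

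| Analysis | p |
|---|---|
| GEE, logit, robust SE, Wald | 5.5e-84 (2e-91 with the arms coded the other way) |
| GEE, logit, bias-reduced SE, Wald | 2e-68 (2e-74 with the other coding) |
| As above, t reference with 18 df | 1e-12 (5e-13 with the other coding) |
| GEE, log link, robust SE, Wald | 2e-101 |
| GEE, logit, model-based SE, Wald | near 1.0 |
| GEE, identity link, robust SE | 0.29 |
| Score (Pearson) test | 0.30 |
| Likelihood-ratio test | 0.23 |
| Fisher's exact test | 1.00 |

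The true estimate is infinite, so the exponents show only where the iteration stopped. The usable content is that p is far below 0.05 in the first four rows and well above it in the rest.

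**Step 3: other layouts.** With 8, 11 or 20 per arm, one event against none (logit, robust) gives p between 4e-82 and 3e-94. With two or three records per patient and a group term, p is about 1e-103. With the SAP's group-by-time terms, baseline cells are empty too. The software then returns undefined or meaningless standard errors, although analytically the interaction p-value tends to zero.

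**Step 4: how often this arises when the arms truly do not differ.** With per-patient risk p, an arm of 10 is empty with probability q = (1 − p)^10. Exactly one arm is empty with probability 2q(1 − q). At 5%, q = 0.95^10 = 0.599, and 2 × 0.599 × 0.401 = 0.48.

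| Assumed risk | Exactly one arm empty | Robust Wald test rejects | Both arms empty |
|---|---|---|---|
| 2% | 30% | 30% | 67% |
| 5% | 48% | 48% | 36% |
| 10% | 45% | 45% | 12% |
| 20% | 19% | 20% | 1% |
| 25% | 11% | 12% | 0.3% |

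The third column enumerates all 10 v 10 outcomes and nearly equals the second, so the false rejections come almost entirely from one-empty-arm data. Fisher's test rejects in at most about 1% across this range.

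**Step 5: what the exact test needs.** Against 0/10, Fisher's p is 0.47 for 2/10, 0.087 for 4/10 and 0.033 for 5/10.

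**The case against.** The strongest reply is that the documents do not commit to the failing version. Section I asks for appropriate models and names no link, variance estimator or test, and some choices give an unremarkable p-value. This stands. A reader might infer that the plan's own rule must declare a difference from one event; the documents support only that the usual form of GEE would do so and that nothing excludes it.

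Second, the 10 v 10 comparison draws on two phases. MAE are defined in Phase I, which the protocol describes as one treated cohort with no arms to compare. The listed Phase II assessments do not include MAE, and the SAP gives no group sizes. A reader might infer that a 10 v 10 test of deaths in hospital patients is specified. It is not: that requires assuming that the SAP's CG and IG are of about that size. The assumption affects how often an arm is empty, but not the failure itself, which appears at 8 to 20 per arm.

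Third, a reader might take the chance that at least one arm is empty (84%, 58% and 11% at 5, 10 and 25% risk) as the risk of a false result. That overstates it, because two empty arms show no difference. Exactly one empty arm is the relevant event.

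Finally, Section G2 already requires frequencies and percentages, so counts would sit beside any p-value, and MAE is one secondary outcome in a convenience-sized pilot. Both points lower the severity. Neither supplies a valid test or resolves the conflict between Sections F2 and I.

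**Conclusion.** The concern holds with its condition attached, as a should-fix. Section I assigns MAE to a GEE test while Section F2 only tracks them. Under a logit or log link with a robust standard error and a Wald test of group, one event against none is reported as overwhelming evidence, and the usual small-sample correction does not repair it. Other settings on the same data give p from about 0.3 to 1.0, so an unspecified software choice decides the result.

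The size depends on two assumptions: about 10 per arm, and an event risk that the documents do not give. Over assumed risks of 2 to 25%, the false-positive rate runs from about 12% to 48%, against a nominal 5%. No primary outcome, sample size or stopping decision rests on MAE, and the point says nothing about GEE for the continuous outcomes.

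**What to change.** Remove MAE, both the composite and its components, from the mixed-model and GEE sentence in Section I. Wherever arms are compared, report the number of patients with at least one event per arm, overall and by component, counting each patient once per type. Give the risk difference with an exact 95% confidence interval, and use Fisher's exact test only if a test is wanted. Then make Section I and Section F2 (Phase I Aim 2) agree on whether MAE are tested or only described, and state which groups and phase any comparison concerns.

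The cost is a sentence or two of wording and no new data. The drawback is that the exact test is conservative: against 0/10, significance at 0.05 needs 5/10 events in the other arm (p = 0.033). That is a fair account of what groups of this size can show.

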Title: Electrical Stimulation Therapy for Preventing Hospital-acquired Weakness in Critically Ill COVID-19 Patients - A Proof of Concept Randomized Controlled Trial

Identifier: NCT04685213

Date: May 21, 2021

Statistical analysis plan

Shapiro-Wilk test ($p > 0.05$) was used to assess the normality of data. Independent t-test was used for group comparison at baseline on normally distributed continuous demographics, clinical data, and sEMG parameters. Mann-Whitney U test was used if the assumption of normal distribution was not satisfied. For categorical variables, Chi-square test was used to compare between-group differences at baseline. The effect size for baseline continuous and categorical data were measured using Cramer's V and Cohen's d, respectively. Generalized estimating equations (GEE) was used to test the main effect of group (two levels: CG and IG), time (three levels: baseline, 3 days, and 9 days), and their interaction on the outcome measures regardless of data unable to obtain due to the patients' critical condition. Pearson correlation was used to associate baseline values with %change of outcomes at 9 days. For those significant associations, multiple linear regression was used to determine the relationship between those significantly associated variables. The model performance was reported in terms of variance (R^2), and p-value. For all tests, an alpha level of < 0.05 was considered statistically significant.

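### The SAP tests every outcome by GEE with no small-sample correction, where the protocol assigns linear mixed models to continuous outcomes; if the usual robust Wald chi-square test is used at about 10 per arm (assumed), the nominal 5% becomes 10.8% for group-by-time and 7.9% for group.

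*SAP*

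**What the plan says.** The SAP is one paragraph. For the treatment comparison, "Generalized estimating equations (GEE) was used to test the main effect of group (two levels: CG and IG"), time (baseline, day 3, day 9) and "their interaction on the outcome measures regardless of data unable to obtain due to the patients' critical condition". The threshold is general: "For all tests, an alpha level of < 0.05 was considered statistically significant". The paragraph gives no working correlation, no choice between robust and model-based variance, no reference distribution, no small-sample correction and no number per arm.

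Section I of the protocol says: "Appropriate mixed models (linear for continuous or Generalized Estimating Equations (GEEs) for non-continuous or non-parametric variables) will be used". Its primary outcomes include "muscle function (assessed using sEMG), and tissue oxygenation (assessed using Kent Imaging"), along with vibration perception threshold, all measured on continuous scales.

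For baseline comparisons the SAP does split by distribution. A t-test applies to "normally distributed continuous demographics, clinical data, and sEMG parameters", and "Mann-Whitney U test was used if the assumption of normal distribution was not satisfied". No such split is made for the GEE.

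The only two-group split with stated sizes is in protocol Section F2, Phase II: "Group 1 (intervention, n=10") against a control group of the same size. Section F1 describes Phase I as 20 hospital patients who all receive stimulation. Section G1 gives 40 in total, chosen by convenience.

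**The concern.** GEE inference with a robust (sandwich) variance relies on many independent subjects. With few, the variance estimate is too small and too variable, and a chi-square reference ignores both defects. The test then rejects a true null more often than stated, and its intervals are too narrow. A model-based variance avoids that problem only if the working correlation is close to the truth.

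The SAP leaves all these choices open in a trial whose samples are of the size where they matter. A reader who sees p < 0.05 cannot tell what error rate lies behind it. The protocol had already named, for continuous outcomes, a method with well-established small-sample inference, and the SAP drops it without comment.

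**Working it through.** **Inputs.** Alpha 0.05 and three visits (SAP), so group has 1 df, and time and group-by-time have 2 df each. Two-sided testing (protocol G2). The number per arm, n, is not given for this comparison. I take n = 10 (the 20 hospital patients of Phase I split equally) as an assumption, and n = 20 (all 40 pooled, which nothing plans) as an upper bound. N = 2n. The documents contain no power or sample-size calculation to reproduce; the only stated figure is the nominal 0.05.

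**Setting.** Complete normal data, equal arms, common covariance, and a full group-by-time mean model. The GEE estimates are then the arm-by-visit means, whichever of working independence or exchangeable is used, and the robust variance is (n-1)/n times the unbiased one.

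**Group-by-time, 2 df, robust Wald chi-square.** The Wald statistic is Hotelling's T2 on the two changes, times n/(n-1). Hence P(reject) = (1 + c/N)^(-(N-3)/2), with c = 5.991.
- N = 20: (1 + 5.991/20)^(-8.5) = 1.2996^(-8.5) = 10.8%.
- N = 40: (1 + 5.991/40)^(-18.5) = 1.1498^(-18.5) = 7.6%.

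**Group main effect, 1 df, robust Wald chi-square.** P(reject) = P(|t| on N-2 df > 1.960 x sqrt((n-1)/n)).
- n = 10: P(|t18| > 1.859) = 7.9%.
- n = 20: P(|t38| > 1.910) = 6.4%.

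**Corrected tests, same setting.** Kenward-Roger with unstructured covariance reduces to Hotelling's test for group-by-time, so its size is 5.0%. Mancl-DeRouen multiplies the robust variance by (n/(n-1))^2. With F(2, N-2), whose critical value doubled is 7.109 or 6.490, the T2 cut-off at n = 10 is 7.109 x 10/9 = 7.899, and the size is (1 + 7.899/18)^(-8.5) = 4.5%. At n = 20 it is 4.7%.

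**Model-based variance, working independence.** Take a true exchangeable correlation of 0.5 (assumed). The variance of the visit-averaged group difference is 1 + 2 x 0.5 = 2 times what the model assumes, so in large samples P(|Z| > 1.960/sqrt(2)) = P(|Z| > 1.386) = 16.6%. The variance of the interaction contrasts is 1 - 0.5 = 0.5 times what the model assumes, so P(chi-square on 2 df > 5.991/0.5) = exp(-5.99) = 0.25%. Simulation at these sample sizes, with correlation exchangeable 0.5 or AR(0.7), gives 17-20% and below 1%.

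| Test at nominal 5% | 10 per arm | 20 per arm |
|---|---|---|
| Robust chi-square, group-by-time | 10.8% | 7.6% |
| Robust chi-square, group | 7.9% | 6.4% |
| Robust with F(2, N-2), group-by-time | 7.5% | 6.2% |
| Model-based, exchangeable, group-by-time (simulated) | about 6-7% | about 5.5-6% |
| Model-based, independence, group-by-time (simulated) | below 1% | below 1% |
| Model-based, independence, group (simulated) | about 17-20% | about 17-20% |
| Mancl-DeRouen with F, group-by-time | 4.5% | 4.7% |
| Mixed model, Kenward-Roger, group-by-time | 5.0% | 5.0% |

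**Skewed outcomes (simulated, log-normal with log-SD 0.5 to 1, assumed).** For group-by-time, robust chi-square rejects 8.4-10.3% / 5.8-7.3%, the mixed model 3.0-4.3% / 3.4-4.7%, and Mancl-DeRouen with F 2.6-3.8% / 3.2-4.3%.

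**The case against.** The strongest reply is that the SAP never says a robust chi-square test was used. A reader might infer that the trial's tests run at about 11%. The documents do not support that: 10.8% is one branch of an unstated choice, it belongs to the 2-df test, and the sentence that names the group effect concerns a 1-df test at 7.9%. Other branches are milder. This stands, and the figures are conditional for that reason. What survives is that the plan permits error rates from below 1% to about 20%.

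Second, the sample size is inferred. It is tempting to take 10 per arm from Phase II, but that phase is home-based with weekly clinic visits over four weeks. The SAP's title and its day 3 and day 9 visits fit the hospital phase, for which the protocol describes no control group. So 10 per arm is an assumption. At the upper bound of 20 the excess is smaller but remains.

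Third, a reader might infer that GEE contradicts the protocol for every outcome. It does not: the protocol allows GEE for non-continuous or non-parametric variables, so GEE for a non-normal outcome agrees with it. The SAP's baseline rule allows for normal sEMG data but does not report that any outcome passed the normality check.

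Fourth, one might read the SAP's remark on unobtainable data as evidence of bias in the treatment effect. No document gives loss rates by arm, so no size can be attached. That is a separate question and should be raised as such.

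Finally, this is a proof-of-concept pilot with several primary outcomes and no stated multiplicity control, so test size is only one contributor to false positives. True, but the plan still declares significance at 0.05.

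**Conclusion.** The point holds in conditional form and should be fixed. The SAP departs from the protocol for normally distributed continuous outcomes and omits the choices that determine the error rate of its GEE tests. If the usual uncorrected robust Wald chi-square test is used, the actual size at 10 / 20 per arm is 10.8% / 7.6% for group-by-time and 7.9% / 6.4% for group. It therefore misses 5% at either sample size considered here. With model-based variance and working independence, the group-by-time test is far too conservative and the group test far too liberal; a reader should not infer that this choice is conservative throughout.

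The robust figures are exact for complete normal data with equal arms and a common covariance. The model-based ones are simulated under assumed correlations. Both rest on an assumed number per arm.

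**What to change.** - For continuous outcomes, use the protocol's linear mixed model: REML, unstructured covariance, Kenward-Roger degrees of freedom, all observed visits. Alternatively, use a GEE with a named working correlation other than independence, a bias-corrected sandwich variance (for example Mancl-DeRouen) and a t/F reference.
- For other outcomes, use that corrected GEE.
- State the phase and the number analysed per arm.
- The SAP is written in the past tense. If the GEE has already been run, keep its result and report the corrected analysis beside it, labelled post hoc.

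**Cost.** SAP wording and a modest re-analysis, with no new patients or data. Relative to the robust z interval, the interval for the difference in day-9 change widens at 10 per arm by sqrt(10/9) x 2.101/1.960 = 1.13 (mixed model) or (10/9) x 2.101/1.960 = 1.19 (Mancl-DeRouen with t). At 20 per arm the increases are 6% and 9%. Apparent power falls: a group-by-time effect that the robust chi-square test would detect 80% of the time is detected 67% / 74% of the time by the mixed model and 65% / 73% by Mancl-DeRouen with F, at 10 / 20 per arm. Part of the 80% was bought with the inflated error rate. Both corrected methods are somewhat conservative for skewed outcomes.
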